## Glossary

Congenital malformation	A morphological defect of an organ, part of an organ, or larger region of the body resulting from an intrinsically abnormal developmental process
Early foetal death	The death of a foetus before completion of 22 gestational weeks (GW)
Ectopic pregnancy	A pregnancy that occurs outside the uterus
Late foetal death	The death of a foetus after the completion of 22 gestational weeks (GW) including stillbirth
Foetal macrosomia	Birth weight above 4 kg
Large-for gestational age	Live born infant with birth weight > 90th percentile for gestational age and sex according to local reference
Major malformations	A life-threatening structural anomaly or an abnormality likely to cause significant impairment of health or functional capacity and which needs medical or surgical treatment. Examples are abnormalities likely to lead to serious handicap or likely to lead to major cosmetic defects (e.g. cleft lip) and which may require major surgery to repair (e.g. atrial septal defect or ventricular septal defect)
Major hypoglycaemia	A hypoglycaemic episode where the patient is not able to treat him/herself and where oral carbohydrates, glucagon or intravenous glucose has to be administered to the patient by another person because of severe central nervous system dysfunction
Minor malformations	Structural anomaly not likely to cause any medical or cosmetic problems
Neonatal death	Death of an infant between 7 days and 28 completed days after delivery
Perinatal death	Death of a foetus/infant between $\geq 22$ completed GWs and $< 1$ completed week after delivery
Pregnancy outcome	The end products of pregnancy which include three main categories: foetal death, spontaneous abortion, and live birth
Pre-term delivery	Delivery before 37 completed gestational weeks
Pre-eclampsia	A condition in pregnancy characterised by new onset of abrupt hypertension (140/90 millimetres of mercury (mm Hg) or greater

documented on two occasions, at least 6 hours but no more than 7 days apart), and albuminuria

Spontaneous abortion      A naturally occurring termination of a pregnancy before 22 completed gestation weeks. Also called miscarriage

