[11](#) and the results are in line with results from a nationwide prospective Norwegian study from 2010 [12](#). In addition, infants of women with DM are 5 times more likely to be stillborn and 3 times more likely to die in their first month of life (neonatal death) compared with those of mothers without DM [11](#). The perinatal death risk is approximately 3% and the neonatal death risk is 0.9% [11](#) and comparable with rates from other European countries [11,13-17](#). Finally, foetal macrosomia is reported to occur in 25–30% and in some studies in more than 40% of the new-borns to mothers with DM [5,7](#).

Pregnant women with DM and with good metabolic control are not more likely than non-diabetic women to lose a pregnancy. This is in contrast to a risk of 15–26% of having a spontaneous abortion in the first trimester for diabetic women who have elevated blood glucose levels [3,8,9](#). As increased perinatal and neonatal death, morbidity and a 2–5-fold increase in congenital anomalies compared with the general population are reported in pregnant women with DM [2](#), further data on the effects of treatment on pregnant women with DM are needed.

Levemir® was approved for treatment of pregnant women with DM in the EU in 2011 [18](#).

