#### 4.2.2.2 Pregnancy outcome endpoints

- Proportion of pregnancies resulting in perinatal death assessed at 1 week after delivery
- Proportion of pregnancies resulting in neonatal death assessed at 4 weeks after delivery
- Proportion of pregnancies resulting in live birth with major congenital malformations and by organ assessed at delivery
- Proportion of pregnancies resulting in live birth with minor congenital malformations and by organ assessed at delivery
- Proportion of induced abortions due to major congenital malformations and by organ assessed at delivery
- Proportion of pregnancies resulting in spontaneous abortion assessed at pregnancy termination
- Proportion of pregnancies resulting in live birth with foetal macrosomia assessed at delivery
- Proportion of pregnancies resulting in live born infants with birth weight > 90th percentile for gestational age and sex (local reference) assessed at delivery
- Proportion of pregnancies resulting in pre-term delivery assessed at delivery

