## 6.3 Exclusion criteria

Women who have been pregnant for more than 16 weeks at baseline visit will be excluded from the study.

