### **8.1.1 Baseline visit**

Signed informed consent must be obtained before any data recording is performed for the purpose of this non-interventional study.

The following will be performed at the baseline visit which will occur as soon as the woman has discovered her pregnancy through a positive pregnancy test:

- Check of eligibility against inclusion criteria (section [6.2](#))
- Check whether the patient has previously participated in the registry (if yes, please state previous patient ID number)
- Demographics (section [8.3.1](#))
- Obstetric history (section [8.3.2](#))
- Maternal medical history (section [8.3.3](#))
- Maternal diabetes history (section [8.3.3](#))
- Current insulin and/or injectable antidiabetic treatment and/or OAD use (section [8.3.3](#))
- Concomitant illnesses (section [8.3.4](#))
- Concomitant medication (section [8.3.4](#))
- Anthropometric measurements (section [8.3.5](#))
- Vital signs (section [8.3.6](#))
- Current pregnancy (section [8.3.7](#))
- HbA1c level assessed according to standard routine at local laboratories (HbA1c level measured  $\leq$  16 weeks prior to baseline visit is acceptable as baseline visit data)

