#### 14.4 Statistical methods

All endpoints will be analysed on the analysis set.

Continuous variables (maternal HbA1c at start of pregnancy, at the end of each trimester, and height and weight of the infant at 1 year) will be summarised with descriptive statistics (number of observations with available values, number of observations with missing values, mean, 95% confidence interval of the mean, standard deviation, minimum, median, maximum), and categorical variables and Apgar score will be displayed in frequency tables (N, %). The mean of the Apgar score will also be computed.

The primary endpoint, proportion of pregnancies resulting in the combined pregnancy outcome will be computed for the Levemir® group, and for the other basal insulin group, the difference between these proportions will be computed along with the 95% confidence interval and the p-value using Fisher's exact test. This simple analysis might be biased if type of basal insulin is confounded with other risk factors for a negative birth outcome, so to take this into account the primary endpoint will also be analysed using logistic regression, see the description below.

This analysis will be performed for all other endpoints which are proportions, both maternal endpoints, pregnancy outcome endpoints, and infants' endpoints at 1 year of age.

In addition, the primary endpoint will be analysed using logistic regression. Both crude and adjusted models will be performed. The model will include treatment group (Levemir®/other basal insulins group), and adjust for potential confounders such as study site, type of DM, race, hypertension, major hypoglycaemic events during pregnancy, folic acid intake, and use of GLP-1 agonists during pregnancy. Furthermore, HbA1c at start of pregnancy, end of first trimester, and end of second trimester, age and BMI of the woman at baseline, duration of DM, blood pressure and previous foetal pregnancy complications will be adjusted for as appropriate. Adjustments will be performed in a stepwise manner, and further specified in the Statistical Analysis Plan. Similar analyses will be performed for all other endpoints which are proportions for maternal endpoints, or proportions for pregnancy outcome endpoints.

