For the infants endpoints at 1 year of age the proportions will also be analysed using logistic regression, the model will include treatment group (Levemir®/other basal insulins group), study site, race, hypertension, major hypoglycaemic events during pregnancy, folic acid intake, and possible use of GLP-1 agonists during pregnancy as factors. Furthermore, HbA1c at start of pregnancy, end of first trimester, and end of second trimester, age and BMI of the woman at baseline, duration of DM, blood pressure and previous foetal pregnancy complications will be included as covariates. The analyses regarding height and weight will also be adjusted for exclusive and/or partial lactation period.

The means of the continuous endpoints (maternal HbA1c at the end of each trimester and, height and weight of the infant at 1 year), will be compared between the Levemir® group and the other basal insulins group using an analysis of covariance (ANCOVA) model.

The incidence of major hypoglycaemia during pregnancy will be computed for both treatment groups.

Additional exploratory hypothesis-generating analyses may also be performed as deemed relevant.

Differences in gestational age at study entry and exact follow-up time will be taken into account in the statistical analysis where relevant.

All statistical analyses will be performed using appropriate statistical software. All statistical tests will be performed as two-sided tests with a significance level of 0.05.

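### Spontaneous abortion gets a crude Fisher comparison that cannot use gestational age at entry, although women enter at any time up to week 16; the promise to account for entry age is tied to no endpoint or method

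*Protocol*

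**What the plan says.** Section 4.2.2.2 defines the endpoint as "Proportion of pregnancies resulting in spontaneous abortion assessed at pregnancy termination", and section 1 lists it among the key secondary endpoints. The Glossary sets the event window: "A naturally occurring termination of a pregnancy before 22 completed gestation weeks".

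Entry is not at a fixed gestational age. Section 8.1.1 describes "the baseline visit which will occur as soon as the woman has discovered her pregnancy through a positive pregnancy test", and section 6.3 sets only an upper limit: "Women who have been pregnant for more than 16 weeks at baseline visit will be excluded from the study".

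Section 14.4 prescribes, for the primary endpoint, a difference in proportions with a 95% confidence interval and Fisher's exact test, and then extends it: "This analysis will be performed for all other endpoints which are proportions, both maternal endpoints, pregnancy outcome endpoints". Crude and adjusted logistic regression is also extended to the pregnancy outcome proportions. The covariates are introduced as examples, and the stepwise adjustment is left to the statistical analysis plan. Gestational age at entry is not named among them.

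Near its end, section 14.4 adds a general commitment, limited to where it is relevant: "Differences in gestational age at study entry and exact follow-up time will be taken into account". It names neither an endpoint nor a method.

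**The concern.** A pregnancy can enter the registry only if it is still continuing at the baseline visit. The later a woman enrols, the more of the risk period she has already passed without a loss. A raw proportion then mixes risks that are conditional on reaching different weeks, and it understates the risk from early pregnancy in both groups.

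Much of that risk lies inside the entry window. Section 3.1 cites "a risk of 15–26% of having a spontaneous abortion in the first trimester for diabetic women who have elevated blood glucose levels". If one group tends to enrol earlier, for example because more pregnancies are planned or because sites differ in referral, it will show more losses even when the true weekly risk is identical. In a post-authorisation safety study this could create a false miscarriage signal or hide a real one. It is left truncation. The bias that section 14.4 itself warns of is confounding by risk factors, which is a different problem.

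**Working it through.** The protocol gives no planning figure for this endpoint, so there is none to reproduce. The check is whether the named test keeps its 5% level when both groups have the same true risk.

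**Inputs from the protocol.** Entry up to week 16 (6.3); events counted to 22 completed weeks (Glossary); first-trimester risk of 15–26% in women with elevated glucose (3.1); two-sided 5% tests (14.4).

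**Assumptions not in the protocol.** The 15% or 26% is treated as the total risk from week 5 to week 22. The hazard is either constant or falls 20% per week. Entry is uniform over the stated weeks among women still pregnant. Group size is 650 or 800. For orientation, section 14.3 needs 1,222/2 = 611 per group for the primary analysis and enrols at least 2,037, so 2,037/2 ≈ 1,018 per group if split equally. The assumed sizes lie between these.

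**Step 1: observed risk by entry week *e*.** With weekly hazard h(w) = c × 0.8^(w−5) for w = 5 to 21, choose c so that 1 − ∏(1 − h(w)) = 0.15. This gives c ≈ 0.033, with 86% of losses before week 13. The risk seen from entry is 1 − ∏(1 − h(w)) taken over w ≥ e. With a constant hazard it is 1 − 0.85^((22−e)/17).

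| Entry week | Falling hazard | Constant hazard |
|---|---|---|
| 6 | 12.1% | 14.2% |
| 8 | 7.8% | 12.5% |
| 10 | 4.9% | 10.8% |
| 12 | 3.0% | 9.1% |

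The true risk is 15% in every row, so the understatement is present whether or not the groups differ.

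**Step 2: two groups with identical hazards.** Average step 1 over each group's entry weeks, then find how often the crude test rejects. For the first row the difference is 0.0822 − 0.0433 = 0.0389 and the pooled proportion is 0.0627. The critical difference is 1.96 × √(2 × 0.0627 × 0.9373/800) = 0.0238 and the standard error is 0.0121. The rejection rate is Φ((0.0389 − 0.0238)/0.0121) ≈ 89%. Simulating Fisher's test itself (1,000 runs) gives 90%.

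| True risk | Entry weeks | Hazard | Observed | Per group | Crude test rejects |
|---|---|---|---|---|---|
| 15% | 6–10 v 8–14 | falling | 8.2% v 4.3% | 800 | about 90% |
| 15% | 6–10 v 8–14 | constant | 12.5% v 10.0% | 800 | 36% |
| 15% | 6–12 v 7–13 | falling | 6.9% v 5.5% | 650 | 19% |
| 15% | 6–12 v 7–13 | constant | 11.7% v 10.9% | 650 | about 7–8% |
| 26% | 6–10 v 8–14 | falling | 14.7% v 7.9% | 800 | 99% |

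**Step 3: methods that use entry time.** In the first and last scenarios, logistic regression with entry week as a linear term rejects in 3.7% and 4.8% of 1,000 simulated studies, with a mean log odds ratio near zero. A further simulation used 800 per group, risks of 15% and 26%, and a constant hazard or one decaying at rate 0.25 per week. A log-rank test with risk sets starting at the week of entry rejected in 3.7–5.4% across all 12 scenarios. Where entry was over weeks 6–10 v 8–12, Fisher's test rejected in 15–91%. With equal entry it rejected in 3.4–4.5%.

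**The case against.** The strongest reply is that the protocol has seen the problem. The closing commitment in section 14.4 names exactly this source of bias, and spontaneous abortion is the endpoint where it is most plainly relevant. The covariate list is open, adjustment detail goes to the statistical analysis plan, and logistic regression with entry week restores the error rate, as step 3 shows. The crude test does not stand alone, and section 5.4 calls the study exploratory.

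Much of this stands. A reader might infer that the plan ignores entry time, or that only a risk-set analysis could give a valid test. The documents and the calculation support neither.

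It is also fair that differential entry is not shown. Section 8.1.1 sets one rule for all women, and section 5.4 asks sites to enrol all registered pregnancies regardless of regimen. The 15–26% applies only to women with elevated glucose; section 3.1 says that women with good control lose pregnancies no more often than women without diabetes.

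Two things remain. Fisher's test is explicitly prescribed for this endpoint and cannot use entry time, however the general sentence is read. And that sentence does not say that it applies here, or how. Left to the shared model, nothing ensures that entry week is included. That model also names HbA1c at the end of the second trimester, to be used as appropriate, a value that cannot exist for a loss before week 22.

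**Conclusion.** The concern holds in a limited form. The prescribed crude comparison estimates no defined risk, understates the risk in both groups, and is biased whenever the groups enter at different gestational ages. With equal true 15% risk and 650 to 800 per group, its false-positive rate runs from about 7–8% to about 90% over the scenarios shown. The range reflects the assumed entry gap, hazard shape, start of risk at week 5 and group size.

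It would be tempting to quote the 90% as the expected error rate, or to say that a false difference will appear. The protocol gives no entry times by group, so neither follows; with equal entry the crude test keeps its level. The point matters because entry times are not controlled by design in a non-randomised registry, and because the remedy uses data already collected.

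**What to change.** - State in section 14.4 that the commitment on gestational age at entry and follow-up time applies to spontaneous abortion.
- Make the main comparison a delayed-entry analysis on the gestational-age scale, with each woman at risk from her baseline visit. Report left-truncated cumulative incidence to 22 weeks with induced abortion as a competing event, and an adjusted cause-specific hazard ratio from a Cox model.
- If logistic regression is kept as the main model, adjust it for entry week as the acceptable minimum. This protects the null comparison, but it gives no interpretable absolute risk and does not handle induced abortion or loss to follow-up.
- Report the crude proportion descriptively, without a p-value.

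The cost is a few sentences and one extra model. Gestational week at baseline (8.3.7) and at termination (8.3.12) is already recorded. The small downside is that risk in the earliest weeks, when few women have yet entered, will be estimated imprecisely.

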#### 3.1 Basic information

The use of insulin analogues has increased significantly in the treatment of both type 1 and type 2 diabetes mellitus (T1DM and T2DM, respectively). Insulin analogues are used in pregnant women with diabetes, as this group has a particular requirement for the safe and efficacious treatment that insulin analogues can deliver. As pregnancy in women with DM is associated with an increased risk of complications for both the mother and the foetus/new-born especially if glycaemic control is outside the target, and as the treatment needs to be adjusted during pregnancy, it is considered a medical challenge to ensure that these women receive the most optimal glycaemic control without inducing hypoglycaemia. If pregnant women receive optimal treatment, it will both increase their own well-being and reduce the overall risk of diabetes complications and pregnancy complications both for the mother and the child. Complications associated most frequently with pregnancies in women with DM include the following :

- Major hypoglycaemia
- Progression of maternal diabetic complications
- Spontaneous abortion
- Pre-eclampsia and pre-term delivery
- Perinatal and neonatal death
- Congenital malformations
- Foetal macrosomia

During recent decades, pregnancy outcomes in women with DM have improved considerably. Hypo- and hyperglycaemia remain, however, a major challenge in the treatment of pregnant women with DM. The proportion of pregnant women reporting major hypoglycaemic episodes that require third party help is as high as 71% . Of these, 33–41% of the episodes additionally require parenteral glucose or glucagon.

The rate of pre-eclampsia in pregnancies in women with DM increases with advanced maternal age, poor glycaemic control and baseline proteinuria . The literature is inconsistent in particular with respect to the rate and severity of pre-eclampsia, but the minimum risk reported in women with DM is 10% .

The most common organs affected by malformations are the central nervous system, heart, skeleton, kidneys, gastro-intestinal tract and lungs. The prevalence of major congenital anomalies in infants of women with DM was 4.5% in a population-based study in England, Wales and Northern Ireland

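### Section 14.4 extends the adjusted logistic regression to the by-organ malformation endpoints, where roughly 3 to 9 major-malformation events per organ cannot support it and Fisher's test has very little power

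*Protocol*

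**What the plan says.** Protocol section 4.2.2.2 lists three pregnancy outcome endpoints that are to be broken down by organ. Two are live-birth endpoints: "Proportion of pregnancies resulting in live birth with major congenital malformations and by organ assessed at delivery" and "Proportion of pregnancies resulting in live birth with minor congenital malformations and by organ assessed at delivery". The third is induced abortion because of a major malformation.

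Section 14.4 describes the unadjusted comparison for the primary endpoint as a difference in proportions with a "95% confidence interval and the p-value using Fisher's exact test". It then widens the scope: "This analysis will be performed for all other endpoints which are proportions, both maternal endpoints, pregnancy outcome endpoints". After describing the crude and adjusted logistic models for the primary endpoint, it widens their scope too: "Similar analyses will be performed for all other endpoints which are proportions for maternal endpoints, or proportions for pregnancy outcome endpoints". The level is common to all tests: "All statistical tests will be performed as two-sided tests with a significance level of 0.05".

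One element is deferred: "Adjustments will be performed in a stepwise manner, and further specified in the Statistical Analysis Plan". The deferral covers how adjustment is done. Which endpoints receive the models is settled in the protocol, and by-organ endpoints are not set apart.

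**The concern.** A by-organ malformation count is a small part of an already uncommon outcome. The protocol nevertheless gives it the same adjusted model as the primary composite. Where events are fewer than model terms, and some levels of a factor have no events, the fit separates and the coefficients run off to infinity. If stepwise selection rescues the fit, the result depends on which few terms happened to survive.

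The unadjusted test is valid at any count but says little at these counts. This is a post-authorisation safety study. A table of organ-specific p-values, nearly all above 0.05 because of the numbers, invites a reader to take them as organ-by-organ reassurance.

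**Working it through.** **Inputs from the protocol**
- Groups: 611 v 611, total 1,222 (section 14.3).
- Currently observed proportion free of all three primary outcomes: 97.3%, so 2.7% with any of them (section 14.3). It is not broken down by outcome.
- Planning rates: major malformation 4.5%, perinatal death 3%, neonatal death 0.9% (section 14.2).
- Organs: section 3.1 names six ("The most common organs affected by malformations are the central nervous system, heart, skeleton, kidneys, gastro-intestinal tract and lungs") and gives no share for any of them.
- Level: two-sided 0.05 (section 14.4).

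**Reproducing the plan's own figure.** The exact Fisher power at 611 v 611 for 93.5% v 97.0% is 79.9%, against the 80% target. So 1,222 is reproduced for the primary endpoint. The protocol states no expected count per organ.

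**Expected major malformations per organ, both groups together.** Six organs with equal shares is my assumption.
- Lower: 1,222 × 0.027 = 33 composite events. Assume malformations make up the same part as in the planning rates, 4.5/(4.5 + 3 + 0.9) = 4.5/8.4 = 0.536. Then 33 × 0.536 = 17.7, and 17.7/6 = 2.9.
- Middle: if all 33 were malformations, 33/6 = 5.5.
- Upper: 1,222 × 0.045 = 55, and 55/6 = 9.2.

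Unequal shares widen this. A 5% share of 17.7 is 0.9 events; a 40% share of 17.7 is 7.1, and of 55 is 22.

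**Events per model term.** Section 14.4 names treatment group, study site, type of diabetes, race, hypertension, major hypoglycaemia, folic acid, GLP-1 agonist use, HbA1c at three times, age, BMI, diabetes duration, blood pressure and previous foetal complications. That is 16 terms, counting each factor once.
- 2.9/16 = 0.18 events per term.
- 9.2/16 = 0.57 events per term.

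Study site has many levels, so the true number of parameters is larger. With site as a fixed factor, any site with no event in that organ has no finite estimate. With about nine events at most nine sites can have one, so ten or more sites guarantee this. The number of sites is not stated.

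**What Fisher's test can show at 611 v 611, two-sided**

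| Split | p |
|---|---|
| 3-0 | 0.249 |
| 4-0 | 0.124 |
| 5-0 | 0.062 |
| 6-0 | 0.031 |
| 7-1 | 0.069 |
| 8-1 | 0.038 |
| 9-0 | 0.004 |

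With five or fewer events no split reaches 0.05. With nine events, at least 8-1 is needed.

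**Chance of reaching six events, and power.** Counts are taken as Poisson with the means above. For power, one group has the rate mean/1,222 and the other two or three times that rate.

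| Mean events per organ | Chance of 6 or more | Power, rate doubled | Power, rate tripled |
|---|---|---|---|
| 2.9 | 8% | 2% | 10% |
| 5.5 | 47% | 8% | 27% |
| 9.2 | 89% | 16% | 50% |

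**The case against.** A reader might infer that every by-organ test is bound to be non-significant because each organ will have about three events. The documents do not support that, for four reasons.
- Three per organ rests on the observed rate continuing, an assumed malformation share and equal organ shares. At the protocol's own 4.5% the mean is about nine, and 8-1 is then significant. A common organ could pass six events even at the lower rate.
- The arithmetic covers one of the three by-organ families. Minor malformations are outside the primary composite. Induced abortions are defined as before 22 completed weeks, so they fall outside the 1,222. Neither has a stated rate.
- The six-event threshold belongs to a split near 1:1. At the 611 v 1,222 split of section 14.2, 3-0 in the smaller group gives p = 0.037. Section 6.1 closes recruitment on the Levemir count and sets no matching limit on the comparator.
- Low power is not impossibility.

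A second stronger reading is that Fisher's test should be dropped for these endpoints. That is a preference. The test stays valid in sparse tables, can flag a 6-0 or 8-1 cluster in a safety study, and already comes with a difference and a 95% interval.

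It can also be said that the adjusted model belongs to the statistical analysis plan, since some covariates are added only as appropriate and the stepwise details are deferred. This stands in part: the plan may cut the covariate list. But the protocol itself fixes that by-organ proportions get these models, and a plan that left them out would depart from it.

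**Conclusion.** The point holds for the adjusted logistic regression. As written, section 14.4 commits the by-organ malformation endpoints to it. For live births with major malformations, about 0.2 to 0.6 events per named term makes the full model unusable across the whole range of assumed counts.

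For Fisher's test the conclusion is weaker: the test is valid but nearly uninformative. Power for a doubled rate is about 2% to 16%, and at 1:1 an organ with five or fewer events cannot reach 0.05. A non-significant organ row therefore carries no reassurance.

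These sizes rest on 611 v 611, equal shares over six organs and, for the lower figure, malformations making up 4.5/8.4 of the observed events. Nothing is claimed on the size of the problem for minor malformations or induced abortions. The primary analysis is not affected.

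**What to change.** In section 14.4, and in the statistical analysis plan to match:
- Exclude the by-organ malformation endpoints from the adjusted logistic regression, and keep adjusted models for the all-organ totals. Even there, 17.7/16 = 1.1 to 55/16 = 3.4 events per named term argue for a short covariate list, which the statistical analysis plan can set.
- For each organ, report counts per group and the between-group difference with an exact 95% confidence interval.
- Label any by-organ Fisher p-value as descriptive, and state that non-significance is not evidence of organ-specific safety.

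The cost is a sentence or two in the protocol and the same in the statistical analysis plan, with less analysis work. The downside is that there will be no adjusted by-organ estimates, so confounding cannot be addressed at organ level.
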